#### 8.6.2 Primary Efficacy Sensitivity Analysis

The ANCOVA-based primary efficacy analysis will be repeated using the mITT set and the PP set.

The ANCOVA-based primary efficacy analysis will be repeated on the full analysis set using last observation carried forward (LOCF) in place of multiple imputations for the handling of missing data.

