
Effective Date: Date of final electronic approval

Baseline will be characterized with descriptive statistics (mean, SD, and 95% CI) for each treatment group.

**Primary Efficacy Sensitivity Analysis:** The ANCOVA-based primary efficacy analysis will be repeated using the modified intent-to-treat (mITT) set and the per protocol (PP) set.

The ANCOVA-based primary efficacy analysis will be repeated on the full analysis set using last observation carried forward (LOCF) in place of multiple imputation for the handling of missing data.

OAT and PAT (USA Only)

OAT and PAT results will be summarized by using descriptive statistics.

Proportion and counts of successful single injections out of total number of single injections using the MOD-4023 PEN in USA patients at Wks 1, 2, 3, 4, 5, and 6, based on the PAT will be reported. Similarly, counts and proportion of successful single injections out of total number of single injections using the MOD-4023 PEN in USA patients at Wk 1, based on the OAT will be reported. Details on the criteria constituting a successful single injection based on OAT and PAT, along with statistical methods to be used for descriptive summaries will be included in the SAP.

Comments on the PAT and OAT related to successful or unsuccessful injection attempts

The written comments provided on the PAT and OAT for successful or unsuccessful injection attempts will be listed. Any other written comments will also be listed.

Information gained by inspection of returned devices

Summary of the information gathered by inspecting the returned devices will be reported.

The QoLISSY core total score at Baseline, 12 months and change from Baseline to month 12, for each group will be summarized using descriptive statistics. This will be done for specific countries as listed in the [Appendix L](#).

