### 8.3 HANDLING OF MISSING DATA

The method for handling missing data will be described in the SAP. The primary method of imputation will be with multiple imputation assuming missing at random, using SAS PROC MI. Details on all sensitivity analyses related to the handling of missing data will also be provided in the SAP.

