### 8.4 ENDPOINTS

#### 8.4.1 Primary Efficacy Endpoint

The primary efficacy endpoint during the main study is the Annual HV in cm/year after 12 months of treatment.

*HV (cm/year) at Visit 8 (12 months)*

$$= (Ht \text{ at Visit } 8 - Ht \text{ at Visit } 2) / ((Date \text{ of Visit } 8 - Date \text{ of Visit } 2) / 365.25);$$

where Visit 2 is the Baseline visit.

(Note: HV at any other post-baseline *Visit xx* is also computed using formula above by replacing *Visit 8* with *Visit xx*).

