### 8.5 STATISTICAL ANALYSIS

The main study database will be cleaned and locked for analysis after the last patient completes 12 months treatment.

The assessment of safety during the LT-OLE will be based on descriptive statistics and summarized by patient's treatment in the treatment period, and overall. No hypothesis testing will be performed. The descriptive statistics will include means, standard deviations, quartiles/ranges for continuous variables, and counts with percentages for categorical data. 95% CI will be used to further describe the clinical/auxological and biochemical endpoints.

The Sponsor reserves the right to stop enrollment when the targeted number of randomized patients is reached. If this situation arises, non-randomized patients that are undergoing Screening will be considered a Screen Failure.

Details of applicable statistical methods for the main study and LT-OLE will be provided in two separate SAPs prior to database lock of the main study and final study closure of the LT-OLE.

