#### 8.6.1 Secondary Endpoint Analyses

A similar ANCOVA model as used for the primary endpoint will be used to analyze:

- annualized HV at 6 months;
- change in Ht SDS at 6 months;
- change in Ht SDS at 12 months.

Least square mean estimates for the 2 treatments and the 95 % CI of the difference between the treatments will be presented.

Descriptive statistics will also be reported for each of these endpoints.

Descriptive statistics (including univariate 95 % CI) will be reported for BM observed and change from Baseline to 12 months.

Descriptive statistics will be reported for HV and Ht SDS at each visit.

Series plots of mean values +/- SE will be reported for HV and Ht SDS by visit and treatment.

ANCOVA-based statistics will be reported by the categorical terms used in the ANCOVA model: age group, gender, peak GH levels, and region.

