#### 8.6.5 LT-OLE Analysis

During the LT-OLE the primary goal of this safety and efficacy analysis is to report on the effect of long-term treatment on Annual HV and other auxological/clinical and biochemical measures.

- Annual HV will be summarized with descriptive statistics each year of LT-OLE treatment. For patients who discontinue without annual measurement, their HV will be calculated based on their last available measure.
- Change in Ht SDS every 12 months (the last value within each year compare to the value 12 months earlier) will be summarized with descriptive statistics.
- Change in bone maturation (BM) every 12 months, (compared to Week 52 BA (calculated as BA/CA) at completion of LT-OLE year 1 and to previous values from LT-OLE year 2 onwards).
- IGF-1, IGF-1 SDS, IGFBP-3 and IGFBP-3 SDS will be summarized with descriptive statistics at each visit. A summary of the incidence of IGF-1 SDS >2.0 at each visit will be provided.

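### LOCF is the only alternative to missing-at-random imputation that the protocol names, and it cannot show how much slower missing MOD-4023 children would have to grow before non-inferiority fails

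*Protocol*

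**What the plan says.** Protocol 8.3 sets the primary method: "The primary method of imputation will be with multiple imputation assuming missing at random, using SAS PROC MI". It applies to the full analysis set, which is everyone randomized (8.2.2).

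Protocol 8.6.2 lists three repeats of the primary ANCOVA: on the mITT set, on the PP set, and on the full analysis set "using last observation carried forward (LOCF) in place of multiple imputations for the handling of missing data". The synopsis, under Primary Efficacy Sensitivity Analysis, says the same: "last observation carried forward (LOCF) in place of multiple imputation for the handling of missing data".

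The protocol does not state what LOCF carries. Annualized HV at the last visit is the natural reading, for three reasons:
- 8.4.1 notes that HV at any other post-baseline visit "is also computed using formula above by replacing" Visit 8 with that visit.
- 8.6.1 adds: "Descriptive statistics will be reported for HV and Ht SDS at each visit".
- For the extension, 8.6.5 says: "For patients who discontinue without annual measurement, their HV will be calculated based on their last available measure".

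Further detail is deferred. Section 8.3 states: "Details on all sensitivity analyses related to the handling of missing data will also be provided in the SAP". Section 8.5 says that the statistical methods "will be provided in two separate SAPs prior to database lock of the main study" and closure of the extension. The SAP supplied is the extension one. It has no hypothesis testing (SAP 5.1), does not impute missing post-baseline efficacy data (5.3) and marks sensitivity analyses as not applicable (6.1.2).

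**The concern.** Non-inferiority here means ruling out a deficit of more than 1.8 cm/year. The useful missing-data question is one-sided: how much worse than imputed would the missing MOD-4023 children have to grow before the claim fails? The mITT and PP repeats change who is analysed and leave the missing-data assumption as it was. LOCF changes the assumption, but to one in which the velocity seen on treatment lasts to Month 12 even in a child who has stopped. A reader who sees MAR and LOCF agree learns little about the unfavourable case. The trial is open-label, so the number of children lost and their reasons for leaving could differ by arm, which makes it worth fixing this check in advance.

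**Working it through.** **Inputs.** From Protocol 8.1: two-sided alpha 0.05, 80% power, SD 2.5, margin -1.8, planning difference -0.8, 110 per arm, about 10% dropout. From 1.3.1: 52 of 53 Phase 2 children finished 12 months, so 1/53 = 1.9% did not. Assumed here: equal missingness in both arms, and no precision gain from ANCOVA covariates or from earlier heights.

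**1. The plan's own figure.** n = 2 x 2.5² x (1.960 + 0.842)² / (1.8 - 0.8)² = 98.1, so 99 per arm against 100 stated. At 100 per arm, power is 80.7% (normal) or 80.4% (noncentral t). 110 x 0.9 = 99 completers. The design reproduces.

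**2. Tipping shift.** Let p be the share missing and d the MAR estimate. Lowering every imputed MOD-4023 value by δ lowers the difference by pδ. With the completers' standard error,

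SE = 2.5 x √(2/n), n = 110(1 - p), L = d - t x SE, tipping δ = (L + 1.8)/p.

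At p = 10% and d = -0.8: SE = 2.5 x √(2/99) = 0.355; L = -0.8 - 1.972 x 0.355 = -1.501; δ = 0.299/0.10 = 2.99.

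The shift also widens the MOD-4023 distribution. To allow for this, solve d - pδ - 1.97√(W + B) = -1.8, with W = (2 x 6.25 + p(1 - p)δ²)/110 and B = 2 x 6.25 x n0/(110 x n1), where n0 children are missing and n1 complete per arm. For the same case δ = 2.82: W = 0.1202, B = 0.0126, and -0.8 - 0.282 - 1.97 x 0.3644 = -1.80.

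| Missing | d | L under MAR | δ, completers' SE | δ, with its own spread |
|---|---|---|---|---|
| 1.9% | -0.8 | -1.471 | 17.4 | 13.2 |
| 5% | -0.8 | -1.482 | 6.4 | 5.6 |
| 10% | -0.8 | -1.501 | 3.0 | 2.8 |
| 15% | -0.8 | -1.521 | 1.9 | 1.8 |
| 10% | -0.4 | -1.101 | 7.0 | 6.2 |
| 10% | 0 | -0.701 | 11.0 | 9.3 |

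An actual delta-adjusted imputation (4,000 imputations, 11 missing per arm) gave 2.82 at d = -0.8 and 9.23 at d = 0.

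**3. Does LOCF respond to such a shift?** This was simulated with 10,000 runs, 10% missing at random in each arm, an assumed Genotropin mean of 10 cm/year, and 6-month annualized HV assumed 1 cm/year above the 12-month value. The delta-adjusted column is idealized: it applies the correct shift and carries no imputation noise. Entries are the share of runs declaring non-inferiority.

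| Case | MAR | LOCF, HV carried | LOCF, height carried | Delta-adjusted |
|---|---|---|---|---|
| MAR difference -0.8, δ = 0 | 80% | 83% | 80% | 84% |
| MAR difference -0.8, δ = 3 | 80% | 83% | 80% | 52% |
| True difference -1.8, δ = 3 | 13% | 14% | 18% | 2.7% |

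In the first two rows LOCF does not move when the missing MOD-4023 children grow 3 cm/year slower, whichever quantity is carried.

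**4. How large might a real shift be?** Suppose a child would reach 10 cm in a year on treatment, with growth slightly front-loaded: the gain by fraction t of the year is 10 x f(t), f = (1 + r)t - r x t², r = 0.1 or 0.2. The child stops at t and then grows at an assumed 3-6 cm/year (u). True 12-month HV is 10 x f(t) + u(1 - t). For a Month 6 stop, f = 0.525 or 0.55, so true HV runs from 5.25 + 1.5 = 6.75 to 5.5 + 3.0 = 8.5. MAR would impute about 10, so the shortfall is 1.5-3.25 cm/year. The 2.8-3.0 tipping shift at 10% missing lies toward the upper end of that range. The same formula gives 2.6-5.1 for a Month 3 stop and 0.6-1.6 for a Month 9 stop. At u = 4.5, averaged over both r, the shortfalls at Months 3, 6 and 9 are 3.8, 2.4 and 1.1. Their mean is 2.4, below the tipping shift.

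**The case against.** **Deferral to the SAP.** This is the strongest objection. Section 8.3 reserves the detail of missing-data sensitivity analyses for the SAP, and the main-study SAP is not among the documents. A reader might infer that no missing-not-at-random check was planned. The documents do not support that; they show only that the protocol names none. The narrower point stands, because the protocol chose to name one missing-data alternative and named the less informative one.

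**Precision.** The primary model adjusts for age group, gender, peak GH, region and baseline height SDS, and heights are also taken at Months 3, 6 and 9. Any gain makes the result more robust. If the covariates explained 20-30% of the variance (assumed), the 10% tipping shift would rise from 3.0 to about 3.7-4.1. This stands, and the table is conservative to that extent.

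**Missingness may be low.** The 10% is a dropout allowance, not a forecast of missing 12-month heights. Section 4.5 encourages a 12-month height after treatment stops, and 5.5 gives early leavers the Visit 8 procedures. At the Phase 2 rate the claim is robust. This stands too; a tipping point would demonstrate that robustness, whereas LOCF cannot.

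**LOCF itself does little harm.** It is supportive. With dropout unrelated to growth and HV carried, simulated false non-inferiority at a true difference of -1.8 was 2.0-2.4% with 11 missing in each arm (nominal 2.5%), and 3.1-4.5% under an assumed split of 16 MOD-4023 to 6 Genotropin. A reader might take the 13-18% in step 3 as a flaw in the primary test. It is not: it follows from assuming a 3 cm/year shift in MOD-4023 alone, for which the documents give no evidence.

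**Reversion.** A reader might compare the tipping shift with the error in the carried value. For a Month 6 stop, carried HV is 10.5-11.0, which is 2.25-4.0 above the truth. That mixes scales, because the tipping shift is measured from the MAR-imputed value. The relevant shortfall is 1.5-3.25, and it counts only if MOD-4023 children alone revert. If both arms revert alike, it largely cancels.

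**Conclusion.** The point holds as a limited one. In the protocol, LOCF is the only named departure from MAR imputation, and it does not answer the question that a non-inferiority claim raises. At a difference of -0.8 the tipping shift is about 13-17 cm/year at 1.9% missing, 5.6-6.4 at 5%, 2.8-3.0 at 10% and 1.8-1.9 at 15%; at a difference of 0 and 10% missing it is 9-11. Fragility therefore needs about 10% or more missing 12-month heights together with a difference near -0.8. These figures rest on SD 2.5, 110 per arm, equal missingness and no precision gain. The primary test and the sample size are unaffected. This is a cheap improvement.

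**What to change.** In Protocol 8.6.2, the synopsis and the main-study SAP, before database lock:
- Make the missing-data sensitivity analysis a delta-adjusted multiple imputation on the full analysis set. Lower only the imputed MOD-4023 values in steps (for example 0.5 cm/year) until the lower 95% limit crosses -1.8, and report that tipping point.
- Drop LOCF, or keep it as supplementary with the carried quantity stated.
- If the main-study SAP already contains this check, cite it in 8.6.2 instead.

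Leave the handling of heights taken after treatment stops to the main-study estimand. Entering them as observed data can dilute a difference, which matters for non-inferiority, and should not be settled through this change.

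The cost is wording and a few extra imputation runs, with no new data or patients. The downside is that the result may be shown to be fragile if missingness is about 10% or more and the difference is near -0.8.

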#### 8.6.3 Biochemical Markers Analysis

Descriptive statistics will be reported for observed and change from Baseline for all biochemical endpoints at each visit.

The number and percent of patients who achieved IGF-1 normalization (defined as IGF-1 SDS between -0.5 and 1.5, inclusive) will be summarized. The number and percent of patients who had IGF-1 SDS > 2.0 will be summarized at each visit.

#### 8.6.4 Additional Endpoints Analysis

##### OAT and PAT (USA Patients Only)

OAT and PAT results will be summarized by using descriptive statistics.

The number and percentage of successful single injections for PAT will be summarized overall. A successful single injection for PAT will be based on the questions “Did the dose window show ‘0’ when you finished your injection?” and “Do you believe that a full dose was injected?” The single

injection is considered successful if the subject answers “Yes” to both questions for all attempts on the form. A subject can have multiple successful single injections at one visit.

Intermittent missing observations for the PAT will be imputed as a failure if both the prior and subsequent observations are a failure. Otherwise, intermittent missing observations will be imputed as a success.

The number and percentage of successful single injections for OAT will be summarized overall. A successful single injection for OAT will be based on the question “...did the user successfully inject into an acceptable injection site without physical assistance?” The single injection is considered successful if the observer answers “Yes” to the question for all attempts on the form. A subject can have multiple successful single injections at 1 visit.

The number and percentage of successful single injections for PAT and OAT will also be summarized by age group, sex, and race.

The number and percentage of the number of attempts required to achieve a success will be summarized for PAT and OAT.

Comments on the PAT and OAT related to successful or unsuccessful injection attempts will be listed.

Information gained by inspection of returned devices will be listed.

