**Secondary Objective:**

- To evaluate the safety and tolerability of weekly MOD-4023 administration.
- To demonstrate successful operation (single injection) of the MOD-4023 single patient use, multi-dose, disposable pre-filled pen (PEN).
- Evaluation of participant and observer feedback on MOD-4023 device usability.
- To confirm the correct operation of devices returned for evaluation.

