## 5.9 MOD-4023 DEVICE USABILITY

### 5.9.1 PAT as provided in [Appendix M](#) (USA Only).

The PAT will be used to record all the patient's or caregiver's injections using MOD-4023 PEN at Wks 1, 2, 3, 4, 5 and 6. It will be completed on site at Wk 1 and at home at Wks 2, 3, 4, 5, and 6 by the actual user of the PEN or parent/legal guardian. The PAT will be completed for all injection attempts at Wks 1, 2, 3, 4, 5, and 6 whether the patient was able to complete the injection or not.

At Visit 2, prior to MOD-4023 on site injection, patients and caregivers will be trained to use the device as outlined in the Patient Dosing Instructions Booklet. In addition, patients and caregivers will be trained on the completion of the PAT and instructed the following:

- In any given wk a new PAT will be completed for each PEN used that wk (in some cases more than 1 PEN may be used for full dose administration; in some cases, more than 1 injection from the same PEN may be needed, in which case only 1 PAT is completed for that PEN that wk).
- On Visit 4 (Month 1/Wk 4 [+1 wk]), to bring the completed PATs and confirming proper recording by the study staff.
- To complete the PAT forms (including the first injection) post MOD-4023 weekly injections. The PAT forms completed after Visit 4 will be collected on Visit 5 (3 months).
- To return all used injection devices and PAT forms as defined in the schedule of activities. If the PAT forms are not completely and correctly filled in as determined by the PI, up to 4 additional wks will be added to the PAT assessment time, not to exceed a total of 6 dose administrations.

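### The missing-form rule for the pen questionnaire scores most gaps as successes, and the supplied documents show no observed-only rate beside it

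*Protocol*

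**What the plan says.** Protocol 8.6.4 (OAT and PAT, USA patients) defines a PAT success from two questions: the "injection is considered successful if the subject answers “Yes” to both questions for all attempts on the form". It then gives a two-branch rule for gaps. An intermittent missing observation "will be imputed as a failure if both the prior and subsequent observations are a failure". For every other pattern, "Otherwise, intermittent missing observations will be imputed as a success".

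Protocol 5.9.1 asks for a form for every injection attempt in weeks 1 to 6, "whether the patient was able to complete the injection or not". The week 1 form is completed on site, staff check the forms at Visit 4, and if forms are not properly filled in, "up to 4 additional wks will be added to the PAT assessment time", within a total of six administrations.

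Results are summarised descriptively, overall and by age group, sex and race. The synopsis leaves further PAT methods to the SAP, and Protocol 8.3 does the same for sensitivity analyses on missing data. Protocol 8.5 says the methods for the main study and the extension "will be provided in two separate SAPs". The SAP supplied covers the extension only and has no PAT analysis. The LOCF sensitivity analysis in Protocol 8.6.2 concerns height velocity, not the PAT.

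**The concern.** The rule is not neutral. A failure is imputed only when two neighbouring results both failed, which is rarer than a single failure, so imputed values succeed more often than observed ones. A blank form may also reflect an attempt that went wrong, since failed attempts are meant to be recorded too; the rule would score most such gaps as successes.

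The PAT proportion bears on the secondary objective of showing that the pen operates successfully, together with the observer tool (OAT) and the examination of returned devices. It is listed among the other or additional endpoints, and nothing is tested against it. What is at stake is the reading of a descriptive percentage. On the text supplied, a reader would see one rate and could not tell how much of it was imputed. The rule also leaves a missing final form unaddressed, because that gap has no later neighbour.

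**Working it through.** The documents give no PAT success rate, missing rate or threshold, so there is no stated figure to reproduce. All rates below are assumptions. One form a week for six weeks is assumed, and the prior and subsequent observations are taken as the nearest observed forms on each side.

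**Direction.** Let p be the success probability. With independent weeks, an imputed value is a success with probability 1 − (1 − p)². The excess over p is 1 − (1 − p)² − p = p(1 − p), which is never negative. With correlated weeks and random missingness, P(both neighbours fail) still cannot exceed P(one fails), so the sign holds while the size shrinks.

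**Size, random missingness.** If m is the share of summarised records that are imputed, the lift over observed-only is m·p(1 − p). With 10% of forms missing, about 63% of the missing forms are intermittent, or 6.3% of all forms. Hence m = 0.063 / (0.90 + 0.063) = 0.0654. At p = 0.90 the lift is 0.0654 × 0.09 = 0.59 points. Simulation of six weekly forms per patient agrees:

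| Failure | Missing | Observed-only | Rule | Lift (points), independent | Lift (points), within-patient correlation 0.3 |
|---|---|---|---|---|---|
| 2% | 5% | 98.0% | 98.1% | +0.06 | +0.04 |
| 5% | 5% | 95.0% | 95.2% | +0.16 | +0.11 |
| 5% | 10% | 95.0% | 95.3% | +0.31 | +0.22 |
| 10% | 10% | 90.0% | 90.6% | +0.6 | +0.41 |
| 20% | 10% | 80.0% | 81.0% | +1.05 | +0.73 |
| 20% | 20% | 79.9% | 82.0% | +2.05 | +1.41 |

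**Size, informative missingness.** Assume 20% failures, with forms missing after 40% of failures and 5% of successes.

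- Observed successes: 0.80 × 0.95 = 0.76. Observed failures: 0.20 × 0.60 = 0.12.
- Observed-only: 0.76 / 0.88 = 86.4%, against a true 80.0%.
- An observed neighbour fails with probability 1 − 0.864 = 0.136, and both fail with probability 0.136² = 0.019. So about 98% of intermittent gaps are scored as successes, whatever really happened. Simulation gives 98.2% of the failed attempts in such gaps (83.8% with correlation 0.3).
- Rule: 87.3% by simulation. It adds 87.3 − 86.4 = 0.9 points to observed-only (about 0.2 with correlation 0.3).
- Every missing form as a failure: 76.0%.

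If the on-site week 1 form is always present, the figures become rule 86.2%, observed-only 85.2%, true 80.0% and bound 76.7%. The rule then adds about 1 point.

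Most of the gap between 87.3% and 80.0% therefore comes from the missingness itself: 86.4 − 80.0 = 6.4 points remain without any imputation.

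**The case against.** The best defence has four parts.

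- **The absence may not be real.** The protocol sends PAT methods and missing-data sensitivity analyses to the SAP, and the main-study SAP was not supplied. This stands as a limit: the criticism of the rule rests on explicit text, but the missing observed-only summary can only be claimed for the documents supplied.
- **The shift is trivial in practice.** The PAT covers only US patients in one arm of about 110. US enrolment is not stated. If 10 to 40 such patients are assumed, with six forms each (60 to 240 forms), a lift of 0.59 points is 0.35 to 1.4 forms. The binomial standard error, √(0.9 × 0.1 / n), is 3.9 to 1.9 points. This also stands, and is why the point ranks low. A systematic upward lean is still worth removing when doing so is nearly free.
- **The bound can mislead.** At 10% failure and 10% missing at random, counting every gap as a failure gives 0.9 × 0.9 = 81.0% against a true 90.0%, further off than the rule. True, so it should be labelled as a bound and not replace the main estimate.
- **Safeguards limit the gaps.** With one form a week only weeks 2 to 5 can be intermittent. The Visit 4 check and the extra weeks reduce gaps further, and diaries, returned devices and complaint reports give other traces of a failed attempt. The calculations model neither the check nor the extension, so real gaps may be fewer than assumed. The safeguards reduce the problem but do not remove it.

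The protocol also speaks of observations, not forms. A form can carry several injections and a week several forms, so the unit of imputation is itself open.

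**Conclusion.** The concern holds, at the lowest level of importance. Under random missingness and a stable success rate, the rule cannot lower the expected PAT success proportion relative to observed-only, and normally raises it. For success rates of 90% to 95% with 5% to 10% of forms missing, the lift is roughly 0.1 to 0.6 points; it reaches about 2 points only at 80% success with 20% missing. Under the informative pattern assumed, the rule adds 0.2 to 1 point to an overstatement that observed-only data would mostly share. These sizes rest entirely on assumed failure and missing rates and on one form a week. No test, threshold or primary conclusion is affected. Confidence is medium, mainly because the main-study SAP was not available and may already contain the summaries asked for.

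**What to change.** Make the observed-only proportion the main PAT summary. Beside it, show a bound that counts every missing PAT, intermittent or final, as a failure, and report the number of missing forms by week. The bound is needed because observed-only removes the rule's own lean but not the effect of forms lost after failed attempts. If the present rule is kept, present it as an additional summary and state how many values it imputed as successes. Say also whether the unit is the form or the injection. If the main-study SAP already provides these summaries, pointing to them is enough.

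The cost is a change of wording and one or two table rows. The stated success rate may come out slightly lower, and the bound will look pessimistic when forms are lost for reasons unrelated to the injection.
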